3.2.2. Disposition

Subject disposition will be summarized for all subjects and for subjects categorized as having prior ALKS 5461 exposure and no prior ALKS 5461 exposure. Subjects with no prior ALKS 5461 exposure will be further summarized by the following sub-categories: De Novo (i.e., New Subjects), PLI Failures (i.e., Lead-in Subjects), and Placebo (i.e., Continuing subjects who received only placebo in the antecendent study). The number and percentage of subjects will be summarized for the following:

- Subjects who enrolled in the study
- Subjects in the Safety Population
- Subjects in the FAS population
- Subject who completed treatment (as indicated on the case report form, CRF)
- Subjects who completed the study (as indicated on the CRF)
- Subjects who discontinued from the study

For subjects who prematurely discontinue from the study, the reasons for discontinuation as recorded on the disposition CRF will be presented. Percentage will be calculated based on Safety Population. Disposition for those subjects who had a down-titratration from the ALKS 5461 2/2 mg dose will be summarized similarly.

A listing of disposition will be provided for all subjects.

Additional analysis will include analysis of time to treatment discontinuation for subjects who discontinue from the study. Time to treatment discontinuation will be summarized for those with study discontinuation due to any cause and due to AE as indicated on the disposition CRF. For those subjects who discontinued due to AE or due to any other reason, time to discontinuation will be calculated from the date of the first dose of ALKS 5461 in the ALK5461-208 study (Visit 2), to the EOT visit date. In analysis of time to treatment discontinuation due to AE, subjects who discontinue for other reasons will be censored by day of EOT. The distribution of time to treatment discontinuation will be estimated and graphically displayed by prior ALKS 5461 experience and overall using Kaplan-Meier methods. Time to treatment discontinuation will also be summarized by descriptive statistics.

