2. SAMPLE SIZE AND STATISTICAL POWER CONSIDERATION

Approximately 1,500 subjects will be enrolled in order to achieve at least 100 subjects with 12 months and 300 subjects with 6 months of exposure to ALKS 5461. Subjects will enter from four feeder studies or enter de novo. The antecedent studies included ALK5461-205, ALK5461-206, ALK5461-207, and ALK5461-210.

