3.5. Treatment Adherence Rate and Extent of Exposure

Treatment adherence to the daily dosing schedule of study drug is measured as the rate of actual compared to intended number of doses to be taken during the ALK5461-208 study. Percentage of treatment adherence will be calculated during 52-week treatment period for the Safety Population as follows:

 $\frac{\text{Total tablets taken}}{\text{Total tablets subject should have taken from the first dose date to the last dose date, inclusive}}$

Duration of exposure to study drug is defined as the number of days from the first dose date of study drug taken to the date of the last dose taken during the ALK5461-208 study, inclusive.

Treatment adherence and exposure of study drug will be summarized by prior ALKS 5461 exposure and overall for the Safety Population.

Treatment adherence will be summarized as a continuous measure using descriptive statistics (number of subjects, mean, SD, median, minimum, and maximum) and as a categorical measure using the number and percentage of subjects in each adherence rate category (rounded to the whole number): <70%; $\ge70\%$ to 80%; >80% to 90%; >90% to 100%; >100% to 110%; >110% to 119%; and $\ge120\%$.

The number of subjects exposed to study drug and the average days of treatment will be summarized as a continuous measure using descriptive statistics (number of subjects, mean, SD, median, minimum, and maximum).

The exposure to ADT will be summarized by ADT class (SSRI, SNRI, TCA, MAOI and other) and Preferred Term (ADT name) using descriptive statistics in a similar fashion. In addition, descriptive statistics of mean daily dose of ADT will be summarized by ADT class and Preferred Term.

The descending cumulative exposure of study drug will be categorized as ≥ 1 day, ≥ 1 month, ≥ 3 months, ≥ 6 months, ≥ 9 months and ≥ 12 months, and will be summarized as a categorical measure using the number and percentage of subjects in each category.

The definitions in Table 3 will be used to define cumulative exposure.

Table 3: Definitions to Define Study Drug Cumulative Exposure

	Definition	Programming Derivation
≥ 1 day	≥ 1 day	
≥ 1 month	≥ 23 days (3 weeks)	\geq (365.25/12)-7 days
\geq 3 months	\geq 84 days (12 weeks)	\geq [(365.25/12)x3]-7 days
≥ 6 months	≥ 169 days (24 weeks)	\geq [(365.25/12)x6]-14 days
≥ 9 months	≥ 260 days (37 weeks)	\geq [(365.25/12)x9]-14 days
≥ 12 months	≥ 351 days (50 weeks)	≥ 365.25 -14 days

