3.7.2. Adverse Events

Adverse events will be coded by System Organ Class and Preferred Term using the Medical Dictionary for Regulatory Activities MedDRA version 19.0. The verbatim term will be included in the AE listings. An AE will be considered as a treatment emergent adverse event (TEAE) if it starts or worsens (if present at baseline) on or after the baseline during treatment period. An AE will be considered as a PDEAE if it starts or worsens during the Post-discontinuation Safety Period which is after the last dose date plus 1 day. For the determination of TEAEs during the treatment period, AEs with the greatest severity before the baseline will be used as the benchmark for the comparison of the AEs occurring during the treatment period. For PDEAEs, the greatest severity before or on the last dose date plus 1 day will be used as the benchmark for the comparison of the AEs occurring during the Post-discontinuation Safety Period.

All AEs will be listed by subject. TEAEs / PDEAEs, deaths, serious adverse events (SAEs), AEs leading to study discontinuation will be included in the summary tables. Summary tables will be provided by prior ALKS 5461 exposure and overall for the Safety Population. For AEs leading to study discontinuation or deaths, the AEs will be summarized in the period in which the discontinuation or death occurred. Drug related TEAEs include those scored as definitely related, probably related, and possibly related by the investigator.

The following summary tables will be produced for the treatment period / Post-discontinuation Safety Period by prior ALKS 5461 exposure and overall for the Safety Population:

- Overview AE summary tables (TEAEs / PDEAEs)
- TEAEs / PDEAEs by System Organ Class and Preferred Term
- TEAEs / PDEAEs by Preferred Term in decreasing frequency
- TEAEs / PDEAEs experienced by ≥5% of subjects (in any group) by Preferred Term
- TEAEs / PDEAEs by System Organ Class, Preferred Term, and Severity
- Drug-related TEAEs by System Organ Class and Preferred Term
- SAEs (fatal and non-fatal) by System Organ Class and Preferred Term
- SAEs (fatal and non-fatal) by Preferred Term in decreasing frequency
- AEs leading to study discontinuation by System Organ Class and Preferred Term
- AEs leading to study discontinuation by Preferred Term in decreasing frequency
- TEAEs by System Organ Class, Preferred Term, and Duration of Exposure
- TEAEs by Preferred Term in decreasing frequency and Duration of Exposure

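### As written, the Kaplan-Meier analysis of time to treatment discontinuation leaves completers out, so the all-cause curve must end at 100% and the AE curve is biased upward

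*SAP*

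**What the plan says.** All the relevant text is in SAP 3.2.2 (Disposition).

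- **Population:** "Additional analysis will include analysis of time to treatment discontinuation for subjects who discontinue from the study".
- **Time variable:** "For those subjects who discontinued due to AE or due to any other reason, time to discontinuation will be calculated", running from the first dose in this study to the EOT visit date.
- **Censoring:** the only rule applies to the AE analysis, where "subjects who discontinue for other reasons will be censored by day of EOT". The all-cause analysis has none.
- **Estimator:** the distribution "will be estimated and graphically displayed by prior ALKS 5461 experience and overall using Kaplan-Meier methods". Descriptive statistics of the same times are added.

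The same section says of the disposition counts and reasons that "Percentage will be calculated based on Safety Population". That sentence comes before the time-to-event paragraph and does not govern it. Protocol 14.3 plans only tabulations of completion, discontinuation and reasons. No other section of either document gives completers a place in the risk set or a censoring date.

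**The concern.** A Kaplan-Meier curve of discontinuation shows retention only if those who do not discontinue are counted at risk. Here the population and the time variable are both confined to people who drop out. The all-cause curve then becomes the distribution of dropout times among dropouts, and it reaches 100% whether 10% or 90% of the study is retained. The AE curve is a hybrid: non-AE dropouts are censored, but completers, who were also at risk of an AE discontinuation throughout, are missing. The display by prior exposure would compare only when dropouts left in each group, not how many left.

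The sole objective is long-term safety and tolerability, and these curves are the only planned display of discontinuation by cause over time. An all-cause curve ending at 100% would also sit awkwardly beside the completer counts in the same section.

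There is a smaller gap. The time ends at the EOT visit date, but Protocol 7.3 foresees subjects who will not come back to the clinic, and the SAP gives no date for them. Their number is unknown.

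**Working it through.** The plan states no Kaplan-Meier figure, so there is none to reproduce. The check compares the curve as written with the curve for the Safety Population with completers censored at end of treatment.

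**Inputs from the documents.** Risk set, event and censoring are from SAP 3.2.2. The Safety Population (at least one dose in this study) is from SAP 3.2.1. Treatment lasts 52 weeks, or 364 days. SAP 2 plans about 1,500 subjects "in order to achieve at least 100 subjects with 12 months and 300 subjects with 6 months of exposure to ALKS 5461", and 100/1,500 = 6.7% serves as a floor for completion.

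**Assumptions.** The documents do not give completion at Day 364 (*S*), the share of dropouts due to AEs (*p*) or the hazard shape.

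**1. All-cause curve.** As written, every included subject has the event and none is censored, so the estimate reaches 1 at the last dropout. Before completers finish, for any hazard shape:

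- Safety Population: 1 − S(t)
- As written: [1 − S(t)] / (1 − S)

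The inflation factor is 1/(1 − S): 1/0.5 = 2.0 at 50% completion, 1/0.4 = 2.5 at 60%, 1/0.6 = 1.67 at 40%, and 1/0.933 = 1.07 at the 6.7% floor.

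**2. AE curve, direction.** The estimate is 1 − ∏(1 − d_j/n_j). Removing event-free completers lowers every n_j and leaves every d_j unchanged. Each factor shrinks, so the curve moves up. In 500 random data sets there was no exception.

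**3. AE curve, size.** Take AE dropouts as a constant share *p* of the hazard and G(t) = [S(t) − S]/(1 − S). The Safety Population estimate is 1 − S(t)^p; as written it is 1 − G(t)^p. With a constant hazard, S(182) = √S. For S = 0.5 and p = 0.25:

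- S(182) = 0.707 and G = (0.707 − 0.5)/0.5 = 0.414
- Safety Population: 1 − 0.707^0.25 = 8.3%
- As written: 1 − 0.414^0.25 = 19.8%

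Results at Day 182, p = 0.25 (Safety Population, then as written):

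| Completion | All-cause | AE |
|---|---|---|
| 60% | 22.5% / 56.4% | 6.2% / 18.7% |
| 50% | 29.3% / 58.6% | 8.3% / 19.8% |
| 40% | 36.8% / 61.3% | 10.8% / 21.1% |
| 6.7% (floor) | 74.2% / 79.5% | 28.7% / 32.7% |

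A simulation of 400 trials of 1,500 subjects at 50% completion gave 29.3% / 58.7% and 8.3% / 19.8%.

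**4. Sensitivity at 50% completion.** With *p* from 10% to 40% the AE ratio at Day 182 is 2.3 to 2.5. With a falling hazard (Weibull shape 0.7, p = 25%) it is 2.5.

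**5. Different dropout pattern.** With dropout spread evenly over Days 1–364 and N = 1,500, the AE estimates (Safety Population, then as written) are:

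| Discontinue / for AE | Day 182 | Day 350 |
|---|---|---|
| 30% / 5% | 2.6% / 10.7% | 5.5% / 41.6% |
| 50% / 10% | 5.6% / 12.9% | 12.3% / 47.3% |
| 50% / 20% | 10.9% / 24.2% | 23.0% / 72.2% |
| 70% / 10% | 6.0% / 9.4% | 14.7% / 36.6% |

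The distortion grows late in the year, when few eventual dropouts remain.

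**6. Display by prior exposure.** Suppose completion is 70% in one group and 40% in the other, with constant hazards. All-cause discontinuation at Day 182 is 1 − √0.7 = 16% against 1 − √0.4 = 37%, about 20 points apart. As written it is 0.163/0.3 = 54% against 0.368/0.6 = 61%, 7 points apart.

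**The case against.** The best defence is that this is loose drafting. Kaplan-Meier by group and overall normally implies that completers are censored; they are flagged on the CRF and have an EOT visit; and the dropout-only sentences could be meant for the descriptive statistics and the event time. The dataset specifications, programming specifications and mock figures are separate documents and may contain the rule. Alternatively, the analysis could be deliberately conditional on dropping out, in which case ending at 100% is a property and not an error.

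The intent may well have been conventional. But the text does more than omit a rule: it states a restricted population and gives censoring to one class of subject only. Overall in this SAP means the exposure groups combined, not a wider population. Risk set and censoring are analysis definitions that belong in the SAP. The conditional reading could excuse the all-cause curve, but not an AE curve that censors non-AE dropouts and omits completers.

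Two points stand. First, other summaries would reveal a retention difference. SAP 3.5 reports Safety Population exposure by group ("The descending cumulative exposure of study drug will be categorized as" at least 1 day up to at least 12 months), and SAP 3.7.2 tabulates "AEs leading to study discontinuation by System Organ Class and Preferred Term". What would be lost is the retention curve itself and the timing of discontinuation by cause. Second, the size rests on assumed inputs. The one figure taken from the documents is a minimum exposure target, not a forecast, and it gives ratios of only 1.07 (all-cause) and 1.14 (AE, 32.7/28.7, with the assumed 25% share).

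**Conclusion.** The point holds. Applied as written, SAP 3.2.2 produces an all-cause curve that ends at 100% regardless of retention, and an AE curve above the Safety Population estimate whenever anyone completes. Both follow from the stated population and need no assumption about rates.

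The size does need assumptions. At 40–60% completion the all-cause curve is inflated 1.67- to 2.5-fold, and at 50% completion the Day 182 AE estimate is roughly 2.3 to 2.5 times too high under a constant hazard. Under the even-spread pattern the Day 182 AE ratio runs from about 1.6 (9.4/6.0) to 4.1 (10.7/2.6). If almost everyone dropped out, the effect would be small.

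No test, sample size or decision depends on this descriptive analysis, and the crude tables are sound. It should be fixed because it is the only planned view of discontinuation by cause over time in a long-term tolerability study.

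**What to change.** State in SAP 3.2.2 that both Kaplan-Meier analyses use the whole Safety Population:

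- **All-cause:** the event is discontinuation for any reason; completers are censored at end of treatment.
- **AE:** the event is discontinuation due to AE; completers are censored at end of treatment, and non-AE dropouts are censored as already planned.
- **Dates:** use the last dose date as the event or censoring time, at least where there is no EOT visit. SAP 3.5 already uses that date.
- **Descriptive statistics of dropout times:** keep them, labelled as conditional on discontinuing.

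A cumulative incidence function for AE discontinuation is an optional supplement. Even after the fix, censoring other dropouts puts the Kaplan-Meier estimate somewhat above the crude proportion (12.9% against 10% at Day 364 in the even-spread case with 50% discontinuing and 10% for AE).

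The cost is one or two sentences and minor programming. The completion flag is already on the CRF, so no new data are needed.

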7.3. Subject Withdrawal

Any subject who signs the informed consent form for this study but does not qualify for ALKS 5461 dosing will be considered a screen failure.

A subject may be discontinued from the study at any time if the subject, investigator, or sponsor determines that it is not in the best interest of the subject to continue participation.

Examples of reasons for subject discontinuation may include, but are not limited to, the following:

- Failure to meet eligibility criteria
- Adverse Event
- Lack of Efficacy
- Physician's decision
- Pregnancy (see [Section 8.4.1](#))
- Protocol violation
- Non-compliance with study drug
- Withdrawal of consent
- Lost to follow-up
- Study terminated by Sponsor
- Other

The investigator must maintain a record of all subjects who fail to complete the study. A full explanation of the reason for study discontinuation will be made on the appropriate electronic case report form (eCRF) and/or IxRS. The reason for discontinuation will be documented. If a subject is lost to follow-up, a reasonable attempt to contact the subject must be made and documented.

If a subject withdraws from the study for any reason, any ongoing adverse events (AEs) will be followed until resolution, until deemed stable by the investigator, or until the subject is deemed by the investigator to be lost to follow-up. If, in the opinion of the investigator, it is necessary to monitor a subject beyond the safety follow-up period, the follow-up period may be extended as necessary. In such instances, the sponsor and the investigator will agree to an acceptable follow-up schedule.

In the event that a subject chooses to withdraw from the study, the investigator should make a reasonable effort to ascertain the reason(s) for withdrawal, while fully respecting the subject's rights to do so. Subjects will be asked to return to the clinic for an early termination visit and follow-up visits. The early termination visit should be scheduled within 24 hours of the subject's last dose and will mirror the assessments scheduled to be collected at Visit 14. Following the early termination visit, subjects will be asked to participate in the safety follow-up period as detailed in [Table 3](#). If the subject fails or refuses to return to the study center for clinic visits, an attempt must be made to contact the subject by telephone in order to assess as many safety and

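### SAP 3.2.2 labels the analysis time to treatment discontinuation, but its event is study discontinuation and its end date is the EOT visit

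*SAP*

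**What the plan says.** SAP 3.2.2 (Disposition) plans an additional "analysis of time to treatment discontinuation for subjects who discontinue from the study". The event is given as follows: "Time to treatment discontinuation will be summarized for those with study discontinuation due to any cause and due to AE", taken from the disposition CRF. Time starts at the first dose "in the ALK5461-208 study (Visit 2), to the EOT visit date". For the AE version, "subjects who discontinue for other reasons will be censored by day of EOT". The distribution is estimated and plotted by Kaplan-Meier, by prior ALKS 5461 exposure and overall, and is also summarized descriptively.

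The same section gives treatment completion its own disposition line, "Subject who completed treatment (as indicated on the case report form, CRF", and lists study completion on a different line.

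SAP 3.5 measures exposure differently, from the first dose "to the date of the last dose taken during the ALK5461-208 study, inclusive".

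**The concern.** The label and the event describe different things. Stopping the drug is a tolerability outcome; leaving the study can happen after the drug has been taken as planned. Protocol 8.1 puts a 4-week follow-up, with four clinic visits and seven phone contacts, after the 52-week treatment period, so there is room to complete treatment without completing the study.

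The end date raises a second problem. It depends on a visit that may not take place or may take place late, although the SAP already uses the last dose date elsewhere.

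The sole objective is long-term safety and tolerability, and this is the only Kaplan-Meier analysis planned. As written it would mix follow-up attrition with stopping the drug, leave some early stoppers without a time, and could disagree with the exposure table for the same subjects.

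**Working it through.** The plan states no figure for this analysis, so there is none to reproduce. The check sets the rules side by side and then illustrates their size.

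**Event.** SAP 3.2.2 separates completing treatment from completing the study, yet counts study discontinuation as the event. SAP 3.7.2 assigns AEs leading to study discontinuation to the period in which the discontinuation occurred, and produces those tables for the post-discontinuation period as well as the treatment period. The SAP therefore allows for study discontinuation after treatment has ended. A 52-week completer who leaves follow-up has a study discontinuation and an EOT date at Visit 14 (Day 365 ± 3), so is an event there. If the exit was for an AE, the same subject is an event in the AE curve although no AE stopped the drug.

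**Missing end date.** Protocol 8.2 only encourages subjects who leave early to attend the early termination visit. Protocol 7.3 provides for telephone contact "If the subject fails or refuses to return to the study center for clinic visits", and lists loss to follow-up as a reason for discontinuation. SAP 3.2.2 gives no substitute date, and SAP 7.1 rules out imputation unless indicated.

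**Late end date.** SAP 3.7.8 plans a listing of EOT COWS assessments made more than 2 days after the last dose, so some late EOT visits are foreseen. Those days would count as time on treatment here but not under SAP 3.5.

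**Illustration.** Only the 1,500 planned subjects come from the documents. The assumed ranges are treatment completion 40-60%, completers leaving follow-up 2-15%, and early discontinuers without an early termination visit 10-30%.

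- False events = 1,500 × completion × follow-up loss. Low: 1,500 × 0.40 × 0.02 = 12. High: 1,500 × 0.60 × 0.15 = 135.
- Early discontinuers = 1,500 × (1 − completion): 1,500 × 0.40 = 600 to 1,500 × 0.60 = 900.
- Subjects with no time: 600 × 0.10 = 60 to 900 × 0.30 = 270.

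**Effect on the curve**, with all treated subjects in the risk set and true completers censored at Days 362-368:

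- *False events.* In simulations with constant-rate exit and 2-10% follow-up loss (12-90 false events), the curve before Day 362 does not change. The Day-368 estimate falls as below. It is sensitive because few subjects remain at risk by then. The median time among those counted as discontinued rises by about 1 to 30 days.

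| Completion | Event = stopping treatment | Event = leaving the study |
|---|---|---|
| 40% | 0.40 | 0.30-0.38 |
| 50% | 0.50 | 0.38-0.47 |
| 60% | 0.60 | 0.45-0.58 |

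- *Subjects dropped for lack of a date.* The estimate just before Day 362 is completers / (completers + early discontinuers kept). At 50% completion with 10% missing at random, 750 / (750 + 675) = 0.526; with 30% missing, 750 / (750 + 525) = 0.588. Both compare with a true 0.500. At 40% completion with 30% missing, 600 / (600 + 630) = 0.488 against 0.400.

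The two errors act in opposite directions, so the result could look plausible while both are present.

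**The case against.** The best defence is that the documents use study discontinuation loosely for stopping the drug early. Protocol 8.2 has subjects who discontinue from the study prematurely go on to a follow-up period, so in that usage follow-up comes after discontinuation, and ending time at EOT fits. The CRF is not available to settle it. This makes the wording ambiguous but does not rescue it, because SAP 3.2.2 separates the two completion statuses and SAP 3.7.2 allows discontinuations in the post-discontinuation period.

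Several stronger readings are tempting, and the documents do not support them:

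- *That this is the only time-based tolerability summary.* SAP 3.5 plans cumulative exposure from at least 1 day to at least 12 months, measured to the last dose. SAP 3.7.2 plans TEAEs by exposure interval and TEAE duration.
- *That the whole curve is wrong because of the false events.* They fall only at about Days 362-368.
- *That late visits are common.* Protocol 7.3 and the footnotes to Protocol Table 2 place the early termination visit within 24 hours of the last dose. SAP 3.7.8 treats later assessments as exceptions to be listed.
- *That the protocol expects many missed visits.* The sentence in Protocol 7.3 is conditional and concerns clinic visits generally.
- *That no fallback date exists anywhere.* SAP 6 and 8 put dataset and programming specifications in separate documents, which may contain one.

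It is also fair that a last dose date can be uncertain. Adherence is checked by pill count and subject query, so a subject who never returns may have no confirmed last dose.

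**Conclusion.** The point stands as a mismatch between a stated endpoint and its stated event and end date. Under the rule as written, treatment completers who leave follow-up become treatment discontinuations at about Day 365, subjects without an EOT visit have no assigned time, and late visits add off-drug days. The illustrative sizes are 12-135 false events and 60-270 subjects without a time. These rest wholly on assumed rates, and the curve effects also on the simulated exit pattern and on visits missing at random. Off-drug days are not quantified and should be uncommon under the 24-hour rule.

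The analysis is descriptive, so no error rate or sample size is affected. The correction is still worth making: the rule is explicit, the better date is already in the SAP, and a retention curve in a long-term tolerability study should measure stopping the drug. Deciding who enters the risk set and how completers are censored is a separate matter; settling it would not correct the event or the date.

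**What to change.** In SAP 3.2.2:

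- Define the event as not completing treatment, from the CRF treatment-completion item already listed there.
- For subjects who did not complete treatment, take the reason (any cause, or AE) from the disposition CRF. The documents do not show that a separate reason for stopping treatment is collected.
- Define time as last dose date − first dose date + 1, matching the inclusive count in SAP 3.5. Where there is no EOT visit, use the last known dose date.
- Do not count treatment completers who leave during follow-up as events; show them in their own disposition row.

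The cost is a few sentences and a small programming change, since the last dose date is already needed for exposure and for the AE treatment period. The remaining weakness is that the last dose date may be uncertain for subjects who never return.

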Safety: Safety and tolerability analyses will be performed using data from the safety population, defined as all subjects who receive at least 1 dose of ALKS 5461. Reported AE terms will be coded using the Medical Dictionary for Regulatory Activities (MedDRA®) preferred terms and system organ class categories.

Safety assessments will be summarized using descriptive statistics along with supportive listings.

Efficacy: Exploratory evaluation of treatment effect over time will be performed using data from the full analysis set (FAS), defined as all subjects who receive at least 1 dose of ALKS 5461 and complete at least 1 post-baseline efficacy assessment (MADRS).

Pharmacokinetics:

Plasma concentration data for BUP, samidorphan, and relevant metabolites as well as background ADTs will be listed and summarized. Additionally, concentration data obtained from this study may be combined with data from other studies for population PK analysis, which will be reported separately.

Sample Size Considerations:

It is estimated that approximately 1,500 subjects will be enrolled in order to ensure that a minimum of 100 subjects achieve 12 months of exposure to ALKS 5461 and a minimum of 300 subjects achieve 6 months of exposure.

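### The Kaplan-Meier curve for discontinuation due to AE censors stops for other reasons, which are competing events, so it overstates the cumulative proportion stopping for an AE by an amount the documents do not allow one to fix

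*SAP*

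**What the plan says.** SAP 3.2.2 (Disposition) first tabulates disposition and the reasons for premature discontinuation, with this denominator: "Percentage will be calculated based on Safety Population". It then adds a time-to-event analysis, introduced as "Additional analysis will include analysis of time to treatment discontinuation for subjects who discontinue from the study", for two endpoints: discontinuation for any cause and discontinuation due to AE. Time runs from the first dose in this study to the end-of-treatment visit. The estimator is given as follows: "The distribution of time to treatment discontinuation will be estimated and graphically displayed by prior ALKS 5461 experience and overall using Kaplan-Meier methods". For the AE endpoint the censoring rule is: "In analysis of time to treatment discontinuation due to AE, subjects who discontinue for other reasons will be censored by day of EOT".

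Protocol 7.3 (Subject Withdrawal) lists reasons for leaving. Besides AE they include lack of efficacy, physician's decision, pregnancy, non-compliance, withdrawal of consent and loss to follow-up.

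Neither document mentions competing risks or cumulative incidence, and neither says that the AE curve is meant as a cause-specific or hypothetical quantity.

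**The concern.** Censoring is harmless when the censored subject could still have the event and was only not observed long enough. That does not describe these subjects. Once a subject is off study drug for lack of efficacy or withdrawn consent, stopping it because of an AE is no longer possible. Kaplan-Meier removes such subjects from the risk set and in effect assigns them the later AE-stopping experience of those who stayed. The result estimates what would happen if nobody ever left for another reason, and only if leavers would have had the same AE risk as stayers.

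Long-term safety and tolerability is the study's only objective (Protocol 6, SAP 1.1), so a curve of AE discontinuation over 52 weeks is likely to be read as the share of subjects who could not tolerate the drug by each time. Two consequences follow:

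- The end of the curve will sit above the AE-discontinuation percentage in the table beside it, without explanation.
- The curves are drawn by prior exposure. If the two groups leave for other reasons at different rates, their AE curves will separate even when the same proportion of each stops for an AE.

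**Working it through.** **Inputs from the documents.** About 1,500 subjects enrolled (SAP 2, Protocol 14.1); 52 weeks of treatment; the censoring rule and estimator quoted above.

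**Assumptions, because the documents give no rates or timing.** True one-year AE stops 10%; other-reason stops 20% to 60%, spread evenly over 364 days; AE stops spread evenly over a window of 56, 182 or 364 days; completers in the risk set and censored at the end of treatment.

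**Formula.** Let *A* be the proportion stopping for an AE and *B* the proportion stopping for other reasons within the AE window. With both spread evenly over that window, the AE hazard at a fraction *u* of the window is A / (1 − (A+B)u). Integrating from 0 to 1 gives a cumulative hazard of −[A/(A+B)] ln(1−A−B), so

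1−KM = 1 − (1−A−B)^(A/(A+B)).

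The true cumulative incidence is *A*. The same formula results from constant proportional cause-specific hazards over the year.

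**AE stops all in the first 8 weeks.** B = other stops × 56/364.
- Other 20%: B = 3.08%; 1 − 0.8692^0.765 = 10.16%
- Other 40%: B = 6.15%; 1 − 0.8385^0.619 = 10.33%
- Other 60%: B = 9.23%; 1 − 0.8077^0.520 = 10.51%

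**AE stops spread over the year.** B = other stops.
- Other 20%: 1 − 0.70^(1/3) = 11.2%
- Other 40%: 1 − 0.50^(1/5) = 12.9%
- Other 50%: 1 − 0.40^(1/6) = 14.2%
- Other 60%: 1 − 0.30^(1/7) = 15.8%

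**Sampling error for scale.** SE = √(0.10 × 0.90 / 1,500) = 0.77 percentage points, so half an SE is 0.39 points.

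| AE stops fall in | Other stops | 1−KM | Excess (points) | Excess / SE |
|---|---|---|---|---|
| first 8 weeks | 20% | 10.16% | 0.16 | 0.21 |
| first 8 weeks | 40% | 10.33% | 0.33 | 0.43 |
| first 8 weeks | 60% | 10.51% | 0.51 | 0.66 |
| whole year | 20% | 11.2% | 1.2 | 1.6 |
| whole year | 40% | 12.9% | 2.9 | 3.8 |
| whole year | 60% | 15.8% | 5.8 | 7.5 |

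Simulated data with N=1,500 agree: 10.2% to 10.5% for the 8-week window, 10.6% to 12.2% when AE stops run to day 182, and 11.3% to 16.0% over the year. The Aalen-Johansen estimate was 10.0% in every case. With no other-reason stops the two estimators coincide at 10.0%.

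**Comparison by prior exposure.** If both groups truly have 10% AE stops spread over the year, but 20% of one and 50% of the other leave for other reasons, the curves end at 11.2% and 14.2%. The 3-point gap is not a difference in the proportion stopping for an AE.

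**The case against.** The best defence is that the tolerability proportion is already reported correctly. SAP 3.2.2 gives reasons for discontinuation as percentages of the Safety Population by exposure group, and SAP 3.7.2 tabulates AEs leading to discontinuation. When every subject is followed to a stop or to completion, the crude percentage equals the one-year cumulative incidence. The curve is introduced as an additional analysis, Protocol 14.3 asks only for counts and reasons, and no test is planned on it. Kaplan-Meier with other stops censored is also a recognised display of the cause-specific hazard. All of this stands and limits the consequence. It does not rescue the curve: the tables give no time course, and the SAP never says the curve should be read as cause-specific.

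The second objection is that the inflation may be trivial. That also stands. The target dose is reached at Day 8 and dose reduction for tolerability is allowed (Protocol 9.5), so early AE stops are plausible, and in that case the excess can be under half an SE. A reader might infer that the bias always matters against sampling error; the 8-week results above show otherwise.

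A reader might also take the exposure target as a retention forecast and derive a much larger distortion. The Protocol synopsis speaks of "a minimum of 100 subjects achieve 12 months of exposure to ALKS 5461". That is a minimum count of exposed subjects, not expected retention, so it cannot be used that way.

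Finally, the analysis is worded for discontinuers and gives no rule for completers. Read literally, with completers excluded, the same simulations give 15% to 87% for a true 10%. That gap is larger, but it is a separate one: the competing-event problem remains once completers are included.

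**Conclusion.** The point holds for the AE time-course curve and its display by prior exposure. The direction is certain: under the stated rule 1-KM cannot fall below the cumulative proportion stopping for an AE, and it exceeds that proportion whenever an AE stop follows a stop for another reason. The size cannot be determined from the documents. For an assumed true 10%, it runs from about 0.2 to 0.5 points if AE stops are confined to the first 8 weeks, to about 1 to 6 points if they are spread over the year, for 20% to 60% other-reason stops. These figures assume that completers are in the risk set and that other-reason stops are evenly spread.

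A reader might conclude that the study will misreport its AE-discontinuation rate. The documents do not support that, because the disposition and AE tables carry the unbiased percentage. The any-cause curve has no competing event and is sound. The change is worth making because the curve, as planned, will disagree with its own section's table without explanation.

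**What to change.** In SAP 3.2.2, for discontinuation due to AE, replace the Kaplan-Meier estimate with the Aalen-Johansen cumulative incidence, plotted by prior exposure and overall. Use the whole Safety Population, treat discontinuation for any other reason as a competing event, and censor only treatment completers, at end of treatment. Keep Kaplan-Meier for any-cause discontinuation.

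The cost is small: a sentence or two of SAP wording, a standard procedure, and no new data, since the reason and date of stopping are already collected. The AE curve will be lower wherever AE stops follow other stops, and its final value will match the disposition table when all subjects are followed to a stop or to completion. The downside is that it no longer carries the cause-specific interpretation. If that view is wanted, the Kaplan-Meier curve can be kept as a supplement, labelled as cause-specific with other-reason stops censored.
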